8.3 Safety Reporting Requirements and Timelines for SAEs and Certain Other Events

Any SAE must be reported (using the SAE Report Form) to Novavax Product Safety **within 24 hours** of the investigator's first knowledge of the event, regardless of the presumed relationship to the investigational product. The investigator or qualified designee must complete the SAE Report Form, sign, and transmit the completed form to Novavax Product Safety.

Nanoparticle Influenza	Vaccine, Quadrivalent	Confidential	qNIV-E-301 Protocol
Novavax, Inc.	Version 4	.0 – 31 October 2019	Page 54

Initial reports of SAEs may be reported via fax or e-mail. Initial reports **must** be signed (physically or electronically) by the investigator or a qualified sub-investigator and transmitted to Novavax Product Safety **within 24 hours** of site awareness. When additional follow-up information becomes available, a written follow-up SAE Report Form must be completed, signed by the investigator or a qualified sub-investigator, and transmitted as soon as possible. The investigator is responsible for obtaining detailed information to support all SAE reports, including records of inpatient and outpatient care, laboratory reports, and autopsy or medical examiner reports.

The following events must also be reported to the Medical Monitor **within 24 hours** of the investigator's first knowledge of the event:

- Any withdrawal of consent after dosing due to an AE.
- Overdose (of a test article as specified in the protocol with or without an AE).
- Inadvertent or accidental exposure to the test article with or without an AE.
- Medication error (includes the administration of an incorrect treatment, an expired test article, a test article that has deviated from its required storage or refrigeration requirements, or any test article prior to documentation of informed consent).

Novavax will be responsible for notifications of SAEs to the relevant regulatory authorities; investigators will be responsible for IRB notification.

8.4 Severity

All AEs will be assigned severity by the subject and/or investigator (as applicable) according to the TGS. Subjects will also be able to indicate severity for any AEs experienced and record this in their diary according to the same scale. For quick reference, an abbreviated grading scale is provided in Table 5 for visible and non-visible local AEs and for systemic AEs for which severity is based on interference with daily activities and not numeric ranges, and in Table 6 for fever and gastrointestinal adverse events of nausea, vomiting, and diarrhea.

The severity of visually-evaluated local AEs will be a function of size. During the diary period, subjects will monitor the size of visible local AEs at the injection site using the Subject Measurement Tool (Appendix 4) which has concentric circles that correspond to the diameters specified in Table 5. For the purposes of reporting during the solicitation period (ie, Day 0 through 6) the subjects' observations will form the primary data. During clinic visits, investigators may measure any persisting local AEs with a ruler, documenting the size of the reaction at its widest diameter, using the numeric scale provided in Table 5 to assess for severity.

Non-visible local AEs (eg, pain) will be assigned a severity based primarily on interference with daily activities.

Systemic solicited AEs and unsolicited AEs will be assigned a severity grade based primarily on disruption of normal daily activities, with the exception of fever and select solicited gastrointestinal AEs that have their own distinct toxicity grades (Table 6). Medical care-seeking is typically absent for Grade 1 (mild) and often present for Grade 3 (severe) events, but is not the primary determinant of severity, since individuals behave differently in this regard.

Severity of vital sign abnormalities (including oral temperature, which is captured as a continuous variable) will be graded based on established ranges provided in the TGS and reported as an AE using the criteria outlined in Section 8.1.3.

		Definitions for Systemic Adverse	
	Definitions for Loc	cal Adverse Events	Events
Severity Grade	Visual Local AE Size Grading Description	Non-Visual Local AE Grading Description	Systemic AE Grading Description
0 – Normal	Reaction size (greatest single diameter) < 2.5 cm	No noticeable symptom	No noticeable symptom or finding
1 – Mild	Reaction size (greatest single diameter) 2.5 to 5.0 cm	Discomfort or tenderness noticeable, but does not interfere with normal daily activities	Mild symptoms or diagnostic observations; intervention not indicated; no interference with normal activity
2 – Moderate	Reaction size (greatest single diameter) > 5.0 to 10.0 cm	Moderate discomfort or tenderness on firm pressure; causes some limitation of normal daily activities	Moderate symptoms or diagnostic observations; some interference with normal activity, not requiring medical intervention
3 – Severe	Reaction size (greatest single diameter) > 10.0 cm	Severe pain at rest, pain or tenderness immobilizes the injected limb and prevents normal daily activities	Severe symptoms, significantly disrupts or prevents normal daily activities, generally requires medical attention/intervention

 Table 5: Definition of Severity Grading for Adverse Events

Table 6:	Severity	Grade	Definitions	for S	Solicited	Gastrointestinal	Adverse	Events and	Fever
----------	----------	-------	-------------	--------------	-----------	------------------	---------	-------------------	-------

	Gast			
Severity Grade	Nausea	Vomiting	Diarrhea	Fever
0 – Normal	No noticeable symptom	No noticeable symptom	No noticeable symptom	< 38.0
1 – Mild	No interference with activity, or 1 to 2 episodes/ 24-hour period	No interference with activity, or 1 to 2 episodes/ 24-hour period	1 to 3 unformed (loose) stools/24-hour period	38.0 to 38.4
2 – Moderate	Some interference with activity, or > 2 episodes/ 24-hour period	Some interference with activity, or > 2 episodes/ 24-hour period	4 to 5 unformed (loose) stools/24-hour period	38.5 to 38.9
3 – Severe	Prevents daily activity, or requires intravenous hydration	Prevents daily activity, or requires intravenous hydration	≥ 6 loose stools/24-hour period, or requires	> 38.9

	Gastrointestinal Adverse Event			
Severity Grade	Nausea	Vomiting	Diarrhea	Fever
			intravenous	
			hydration	

Table 6: Severity Grade Definitions for Solicited Gastrointestinal Adverse Events and Fever

8.5 **Relationship (Causality)**

The relationship of an AE to the test article must be assessed and documented by the investigator or a qualified sub-investigator. Based on the criteria described below, the investigator must classify the AE according to the following categories shown in Table 7.

Relationship	Relationship Description
Unrelated / Unlikely	• May or may not follow a reasonable temporal sequence from administration of the test article;
	• No plausible mechanism based on known or suspected actions of the test article or product class;
	• Readily explained by known characteristics of the subject's clinical state, common intercurrent illnesses, or other treatments administered to the subject.
Possibly	• Follows a reasonable temporal sequence from administration of the test article;
	• Based on known or suspected actions of the test article or product class, a plausible mechanism could exist;
	• May be reasonably explained by known characteristics of the subject's clinical state, common intercurrent illnesses, or other treatments administered to the subject; but the investigator deems this less likely than test article effect.
Probably	• Follows a reasonable temporal sequence from administration of the test article;
	• Based on known or suspected actions of the test article or product class, a plausible mechanism could exist;
	• Cannot be reasonably explained by known characteristics of the subject's clinical state, common intercurrent illnesses, or other treatments administered to the subject.
Definitely	• Follows a reasonable temporal sequence from administration of the test article;
	• Consistent with known actions of the test article or product class;
	• Cannot be reasonably explained by known characteristics of the subject's clinical state, common intercurrent illnesses, or other treatments administered to the subject.
	• May be confirmed by re-challenge (if applicable).

 Table 7:
 Definition of Relationship for Adverse Events

9 TRIAL DATA MANAGEMENT

9.1 Recording and Collection of Data

Novavax will provide sites with source document templates for the recording and collection of subject data. Data will be entered into an electronic data capture (EDC) system by site staff. All EDC entries will be completed as soon as possible after the subject's visit. Corrections to data in the EDC system will be documented in the electronic audit trail that is compliant to US FDA regulations (21 Code of Federal Regulations Part 11). The investigator will review data resident in the EDC and indicate by electronic signature that, to his/her knowledge, the data are complete and accurate. If further changes are made after this, the investigator will need to again sign the Investigator Signature Page electronically. Designated source documents will be signed and dated by the appropriate trial personnel. The investigator must agree to ensure completion and maintenance of source documents for each subject participating in the trial.

9.2 Data Quality Assurance

All trial data will be entered by clinical trial site staff with trial-specific EDC training into a computerized data management system via EDC. Statistical analyses of data will only be performed after all clinical monitoring and data queries have been resolved.

9.3 Monitoring

Novavax, as the Sponsor of this trial, is responsible for ensuring the proper conduct of the trial, in accordance with the Declaration of Helsinki (Amended Fortaleza, Brazil, 2013) and Good Clinical Practices (GCP) including, but not limited to, protocol adherence and the validity of the data recorded in the database. For the purposes of this trial, Novavax may transfer responsibility for the clinical monitoring to a CRO who may monitor on-site or remotely. Novavax and/or CRO are responsible for ensuring that the site(s) prepare complete, accurate, legible, and well-organized clinical trial data. On-site monitoring inspections will be routinely performed in order to review data entry of source documentation directly captured on paper and transcribed into the system, to ensure protocol adherence, to assess site operational capabilities, and to perform other monitoring activities that cannot be performed remotely. In addition, clinical monitors will provide ongoing support to ensure the investigator's continued understanding of all applicable regulations concerning the clinical evaluation of the investigational vaccine, and the proper execution of the protocol, as well as the investigator's reporting responsibilities.

The clinical trial sites will be monitored periodically for database accuracy and completeness, adherence to the protocol, regulatory compliance, safety reporting, clinical trial material accountability, and the maintenance of comprehensive source documents. When data entry has been completed by the appropriate trial staff, source documents verified and monitored by Novavax and/or CRO representatives, and reviewed by the investigator, the investigator should sign and date the *Investigator Signature Page*.

9.4 Audit and Inspection

Novavax CQA reserves the option to develop a Quality Assurance plan to ensure the integrity of the conduct of the clinical trial. CQA visits may be performed during the trial and post-trial by Novavax CQA or other personnel authorized by Novavax. Regulatory authorities reserve the right to audit trial sites following submission of data in regulatory applications. By signing this protocol, the investigator acknowledges that these inspection procedures may take place and agrees to provide access to the required subject records and other trial documentation. Further, the investigator agrees to inform Novavax and the IRB immediately of any scheduled or unscheduled inspection by regulatory authorities.

9.5 Adherence to and Changes to the Protocol

Any change or addition to this protocol will only be made when a protocol amendment has been written, approved, and signed by Novavax and the investigator before the change or addition can be considered effective, unless immediate implementation of a change is necessary to ensure the safety of subjects. This amendment must also be submitted to the IRB for approval and, when necessary, regulatory authority approval before implementation. Protocol amendments may affect consent forms of current and future subjects. Novavax will clearly specify when a protocol amendment includes safety, procedural, and/or efficacy information that will require specific informed consent form (ICF) text changes.

9.6 Retention of Records

It is the responsibility of the investigator and trial staff to maintain a comprehensive and centralized filing system of all trial-related documentation, which is suitable for inspection at any time by Novavax, its designees, and regulatory agencies. These should minimally include:

- Subject files including the completed eCRF (based on output from clinical database) on compact disc (CD), supporting source documentation, and the informed consent and any other subject information.
- Trial files (essential documents and regulatory files) including the protocol with all amendments, the IB, safety and protocol deviations meeting IRB reportable criteria, copies of all regulatory documentation, and all correspondence with the IRB, regulatory authority, and Novavax.
- Pharmacy files including all investigational vaccine shipment, receipt, storage, dispensing, and accountability records, and pharmacy-related correspondence.

In addition to the eCRF, the investigator will maintain adequate records that fully document the progress of the trial. Copies of these trial records and related documents must be kept on file by the investigator for a period of no less than 15 years (or longer if mandated by relevant local regulations). ALL DOCUMENTATION AND MATERIAL PROVIDED BY NOVAVAX OR A NOVAVAX REPRESENTATIVE FOR THIS TRIAL (CASE REPORT FORMS, PROTOCOL, ETC) ARE TO BE RETAINED IN A SECURE PLACE AND TREATED AS CONFIDENTIAL MATERIAL.

10 TRIAL STATISTICAL CONSIDERATIONS

This section includes a brief description of the statistical analyses that will be performed in this trial.

10.1 Subject Populations

The following subject populations will be used in all analyses:

- Safety Population Includes all trial subjects that provide consent, are randomized, and receive the test article. The Safety Population will be used for all safety analyses; and will be analyzed as actually treated.
- Per-Protocol Population (PP) Includes all subjects in the Safety Population that received the assigned dose of the test article according to protocol, have HAI serology results for Day 0 and Day 28, and have no major protocol deviations affecting the primary immunogenicity outcomes as determined by Novavax prior to database lock and unblinding. The PP Population will be the primary population used for immunogenicity analyses.
- Intent-to-Treat (ITT) Population Includes all subjects in the Safety Population that provide any HAI serology data. The ITT Population will be the secondary population used for any immunogenicity analyses and will be analyzed according to treatment as randomized. Analysis using the ITT population will not be performed if it differs from the PP population by $\leq 5\%$ of the subjects for each of the 2 treatment groups.

10.2 General

Continuous variables will be presented by summary statistics (eg, mean and standard deviation [SD] for the non-immunogenicity endpoints; geometric means and their 95% CI for the immunogenicity endpoints). Categorical variables will be presented by frequency distributions (frequency counts and percentages for the non-immunogenicity endpoints; percentages and their 95% CIs for the immunogenicity endpoints).

10.3 Demographics and Protocol Compliance

Demographic parameters and other baseline characteristics (eg, age, sex, race, and ethnicity) will be summarized by treatment group for all subjects in the safety population. The number and description of protocol deviations will be summarized for all enrolled subjects who signed the ICF and were randomized in to the study.

10.4 Analyses Addressing Protocol Objectives

10.4.1 Analyses of Primary Objectives

10.4.1.1 Immunogenicity

The Per-Protocol (PP) population (ie, randomized subjects who received the assigned dose of the test article according to the protocol, have HAI serology results at Day 0 and Day 28, and have no major protocol deviations) will be the primary population for immunogenicity analysis. A separate intent-to-treat (ITT) population analysis will not be produced unless > 5% of at least

Nanoparticle Influenza	Vaccine, Quadrivalent	Confidential	qNIV-E-301 Protocol
Novavax, Inc.	Version 4	4.0 – 31 October 2019	Page 60

1 treatment group is excluded from the PP population. No missing data will be imputed. For GMTs and GMRs, titers reported below the lower limit of quantitation (LLOQ, ie, below the starting dilution of assay reported as "< 10") will be set to half that limit (ie, 10/2 = 5).

For purposes of determining non-inferiority (and exploratory superiority) in immunogenicity of 240 μ g Quad-NIV co-formulated with 75 μ g Matrix-M1 adjuvant, relative to a US-licensed comparator, Fluzone Quadrivalent, for all Quad-NIV homologous influenza strains (2 influenza A and 2 influenza B strains) at 28 days post-vaccination, derived/calculated endpoints will include:

- Two-sided 95% CIs for the ratio of Day 28 post-vaccination GMTs between Quad-NIV and Fluzone Quadrivalent will be constructed using log normal distribution. The log₁₀ values will be used to construct a CI using the analysis of covariance (ANCOVA) with treatment group and baseline at Day 0 (adjusted for intergroup variation in baseline [pre-vaccination] titers) as the covariates under two-sided type I error rate of 0.05. No type I error rate adjustments will be made. The mean difference and the corresponding CI limits will then be exponentiated to obtain the ratio of GMT and the corresponding CI.
- Two-sided 95% CIs for the difference of the SCRs between Quad-NIV and Fluzone Quadrivalent will be based on the Newcombe hybrid score (METHOD = SCORE riskdiff-option for PROC FREQ in SAS).

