3.3 Randomization and Blinding Procedure

Subject randomization will be conducted using an Interactive Web Randomization System (IWRS). Stratification will be by site, age, and history of receipt of the 2018-19 influenza vaccine. Proportions of subjects in the various strata will not be pre-specified; rather, the goal will be to achieve an approximately equal distribution of subjects with these characteristics across the two treatment groups.

Preparation and administration of each test article dose will be performed by unblinded vaccine pharmacists/administrators. These persons, identified prior to trial dosing, will not perform any trial assessments post-dosing.

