10.5 Sample Size Considerations

This study has a single comparison between Quad-NIV and Fluzone Quadrivalent at Day 28 post-vaccination for the primary immunogenicity objective. No adjustment of the Type I error rate for multiple comparisons is warranted since the simultaneous successes of all 8 comparisons planned for the 4 strains contained in the vaccines and the two endpoints (GMT and SCR) are required for the demonstration of the primary non-inferiority objective of the study.

Non-inferiority is defined as the lower bound of the 2-sided 95% CI on the ratio of GMTs (Quad-NIV vs Fluzone) ≥ 0.67 (ie, unadjusted 1-sided p-value < 0.025 against the null hypothesis of H0: Ratio of GMT < 0.67) and the lower bound of the two-sided 95% CI on the difference of the SCRs (Quad-NIV - Fluzone) $\geq -10\%$ (ie, unadjusted 1-sided p-value < 0.025 against the null hypothesis of H0: Difference of SCRs < -10%).

For the calculation of sample size estimation, we used assumptions of true differences, ie, the ratio of GMTs (Quad-NIV vs Fluzone Quadrivalent) is 1.0 for all 4 homologous strains, and

Nanoparticle Influenza	Vaccine, Quadrivalent	Confidential	qNIV-E-301 Protocol
Novavax, Inc.	Version 4	4.0 - 31 October 2019	Page 62

the difference of the SCRs is -2% for each of the 4 homologous strains, based on the average performance in the previous trial (qNIV-E-201). To achieve an overall 90% power (ie, ~ 97.5% power for each of the 4 strains) to demonstrate a non-inferiority margin for SCR difference of -10%, the SCR of reference group (Fluzone Quadrivalent) is assumed to be 0.5 and the SCR of treatment group (Quad-NIV) is assumed to be 0.48 under the null hypothesis of inferiority (H0: Difference of SCRs < -10%). The significance level of the testing is 0.025. Sample size was estimated to be 1195 in each group by assuming equal size in each group. The sample size accounted for a 10% attrition rate for the per-protocol population such that the primary analysis population for all immunogenicity endpoints will be 1325 in each group.

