12.2 Adjustments for Covariates

Comparison of GMTs between treatment groups will be adjusted for pre-vaccination titer.

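### Randomisation is stratified by age and prior vaccination, but no planned immunogenicity analysis uses either, so a weaker response in adults ≥75 could go unreported

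*Protocol*

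**What the plan says.** Protocol 3.3 states: "Stratification will be by site, age, and history of receipt of the 2018-19 influenza vaccine". Protocol 3.1 gives the age groups as 65 to <75 and ≥75. Section 3.3 also leaves the size of each stratum to recruitment.

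The analysis does not carry these factors forward:

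- **GMT.** Protocol 10.4.1.1 specifies "ANCOVA) with treatment group and baseline at Day 0 (adjusted for intergroup variation in baseline [pre-vaccination] titers) as the covariates". The sample code in SAP 7.1.1 has Day 0 titer and treatment only, and SAP 12.2 confirms: "Comparison of GMTs between treatment groups will be adjusted for pre-vaccination titer".
- **SCR.** The sample code in SAP 7.1.1 is one treatment-by-seroconversion table with a Newcombe interval and no stratum variable.
- **Secondary and exploratory results.** Protocol 10.4.2 and SAP 7.2 list them by treatment group and visit.
- **Elsewhere.** Age and vaccination history appear only as baseline characteristics (SAP 5) and in the check for mis-stratification (SAP 3.4.1).

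Protocol 10.5 describes the primary objective in one line: "This study has a single comparison between Quad-NIV and Fluzone Quadrivalent at Day 28 post-vaccination for the primary immunogenicity objective". Success needs the GMT bound (0.67) and the SCR bound (-10%) to be met for all four strains, which is eight comparisons.

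**The concern.** Protocol 1.7 says the data are meant to support licensure in adults ≥65. The sponsor thought age and prior vaccination important enough to balance at randomisation, but no planned output would show the vaccine comparison within either. The overall result is an average weighted by whoever enrols. If adults ≥75 responded less well to Quad-NIV than to Fluzone Quadrivalent, the younger stratum could offset this in the pooled estimate, and no planned table would show it. Because the Day 28 review (Protocol 10.6.1, SAP 10) opens treatment codes for the primary endpoints, a by-stratum table requested after that would be post hoc.

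**Working it through.** **Inputs from the documents.** One-sided level: "The significance level of the testing is 0.025". Rates: "the SCR of reference group (Fluzone Quadrivalent) is assumed to be 0.5 and the SCR of treatment group (Quad-NIV) is assumed to be 0.48". SCR margin 10 points; GMT margin 0.67; SD of log10 titer up to about 0.4; 1325 randomised per group with 10% attrition.

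**Assumptions, not in the documents.** Share aged ≥75: 30% (range 20 to 40%). Stratum effects as stated in each step. Fluzone SCR of 0.50 in both age groups.

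**1. The plan's own figure.** The plan says "Sample size was estimated to be 1195 in each group by assuming equal size in each group", for a target of "ie, ~ 97.5% power for each of the 4 strains) to demonstrate a non-inferiority margin for SCR difference of -10" points. With unpooled variance:

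n = (1.96 + 1.96)² × (0.50×0.50 + 0.48×0.52) / (0.10 − 0.02)² = 15.37 × 0.4996 / 0.0064 ≈ 1200.

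Using power 0.9^(1/4) = 0.974 gives 1190. The stated 1195 lies between them. At 1195 the power is 0.9746 per strain and 0.9746⁴ = 0.902 overall, so the figure reproduces. Below I use 0.9 × 1325 ≈ 1192 per arm; the difference from 1195 is immaterial.

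**2. GMT criterion alone.** Take a true ratio of 0.60 in ≥75 and 1.0 below 75.

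- SE of ln ratio = 0.4 × ln 10 × √(2/1192) = 0.0377.
- Pooled ratio = 0.60^share = 0.903 / 0.858 / 0.815 at shares of 20/30/40%.
- Least favourable case (40%): [ln(0.815) − ln(0.67)] / 0.0377 − 1.96 = 3.24, a pass probability of 0.9994. The other two round to 1.000.

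**3. SCR criterion.** Take a true difference of −12 points in ≥75 and 0 below 75. Pass probabilities come from exact enumeration of the Newcombe interval.

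| Share ≥75 | Pooled difference (points) | One strain passes | All four pass, if all affected and independent |
|---|---|---|---|
| 20% | −2.4 | 0.961 | 0.961⁴ = 0.85 |
| 30% | −3.6 | 0.880 | 0.880⁴ = 0.60 |
| 40% | −4.8 | 0.721 | 0.721⁴ = 0.27 |

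**4. The two criteria together.** A ratio of 0.60 is a shift of log10(0.60) = −0.222, which would normally lower seroconversion too. Assume a normal log10 fold-rise with SD 0.4 (range 0.3 to 0.6; not in the documents). SCR in ≥75 then falls by 0.50 − Φ(−0.222/0.4) = 21 points (27 to 14). At a 30% share the pooled difference is −6.3 points, and that strain passes the SCR bound 44% of the time (15% to 79%). At SD 0.4 the figures for shares of 20% and 40% are 81% and 12%. With all four strains affected and independent, at 30% and SD 0.4, it is 0.44⁴ ≈ 4%.

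**5. What a ≥75 row would show.**

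- GMT at a 30% share (358 per arm): SE = 0.4 × ln 10 × √(2/358) = 0.0688, so a true 0.60 would read about 0.60 (0.52 to 0.69).
- SCR: the 95% half-width is about 9.0 / 7.3 / 6.3 points at 20/30/40%.
- At the planned true −2 points, the chance that one strain's ≥75 row clears −10% is 42/57/70%. With four independent strains, at least one row would cross −10% in 1 − 0.42⁴ = 97%, 1 − 0.57⁴ = 89% or 1 − 0.70⁴ = 76% of trials with no real problem.

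**6. Covariates.** In simulated stratified trials with assumed effects of 0.1 to 0.3 log10 for vaccination and 0.05 to 0.1 log10 for age, adding both factors multiplied the GMT standard error by 0.990 / 0.961 / 0.927 across three settings. A rough closed form agrees. The SE ratio is about √(1 − Σd²p(1−p)/0.16), where d is a factor's effect and p its share. With vaccination split 50:50 and 30% aged ≥75, the smallest effects give √(1 − 0.0030/0.16) = 0.990 and the largest √(1 − 0.0246/0.16) = 0.920.

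**The case against.** The strongest reply is that the decision rule is joint. Step 2 considers half of it; step 4 shows that a GMT ratio of 0.60 in ≥75 would probably reduce seroconversion enough to fail the pooled SCR bound fairly often. A reader might infer that a failure in adults ≥75 would stay hidden, or that the trial's verdict is almost insensitive to one. The documents do not support that: success needs both bounds for all four strains, and only the GMT bound is that insensitive. This objection stands, and limits the point to a deficit that could pass unnoticed.

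The example rows are also not decisive. The interval 0.52 to 0.69 contains 0.67, and −12 ± 7 points contains −10, so neither would establish inferiority. Chance crossings would be common (step 5). This stands, and is why the table must be labelled as estimation.

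A reader might further infer that the trial cannot examine its strata. It can: age, vaccination history and titers are all collected. What is missing is a pre-specified result.

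On the covariates, GMT power is already close to 100%, Day 0 titer may absorb part of any vaccination effect, and adding them reveals nothing about differences between strata. All true. The case for them is only that the model should match the randomisation. Site, the third factor, is also absent from the model; it is left out of the proposal because the point concerns age and vaccination history.

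Finally, neither document gives evidence that the vaccine effect differs by age.

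**Conclusion.** The omission is confirmed in both documents. Age and 2018-19 vaccination are used to randomise but in no planned immunogenicity result, so a weaker response in adults ≥75 could go unreported whether or not the pooled test passes.

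How easily it passes depends on the criterion. The GMT bound alone almost always passes in the scenario examined. The SCR bound passes in 72 to 96% of trials for one strain at −12 points, in about 27 to 85% if all four strains are affected independently, and less often if a GMT ratio of 0.60 also lowers SCR. All of this rests on an assumed ≥75 share of 20 to 40% and assumed stratum effects.

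A reader might infer that omitting the stratification factors invalidates the primary analysis. It does not: the primary test remains valid, and the GMT interval is slightly conservative. The change is worth making because it is cheap and has to be written down before unblinding.

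**What to change.** In Protocol 10.4.1.1 and SAP 7.1.1; each change stands alone.

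1. **By-stratum table.** Before the Day 28 unblinding, pre-specify a descriptive table of the Day 28 GMT ratio and SCR difference with 95% CIs, for each homologous strain, within 65 to <75, within ≥75, and within 2018-19 vaccinated yes and no. Use the same ANCOVA and Newcombe methods. State that it spends no alpha, leaves N and the success rule unchanged, and is for estimation only. Note beside it that the SCR half-width in ≥75 is about 6 to 9 points, so single-strain rows will often cross −10% by chance.
2. **Covariates.** Add age group and 2018-19 vaccination to the GMT ANCOVA and amend SAP 12.2 to match. The gain is modest: a standard error about 1 to 7% smaller under the assumed effects.

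The cost is SAP and protocol wording and a few tables from data already collected, with no added subjects or procedures. The downside is 16 GMT ratios and 16 SCR differences (4 strains × 4 groups), some of which will look discordant by chance.
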